**ASSIGNMENT TO CONTROL VERSUS INTERVENTION:** The unit of randomization is at the subject (neonate) level. The study statistician will generate a random allocation list and employ allocation concealment to assign eligible subjects with a 2:1 intervention-to-control arm ratio. During the 12-month enrollment (intervention delivery) period, a research coordinator will open the sequentially numbered assignments to invite parents of neonates assigned to the intervention arm to sign up for virtual FCR. Neonates of parents accepting this offer will be considered “subscribed.” For neonates with more than one eligible parent, separate subscription invitations will be used for each parent.

**DELIVERY OF INTERVENTION:** We will use Extended Care as the software interface for virtual FCR. This secure platform meets HIPAA security rules and launches from the electronic health record. Parents will use the Extended Care application on their personal computer or smart device. The NICU medical team will use Extended Care on a computer on wheels with a speaker and camera. Virtual FCR will be available for parents of subscribed neonates to attend Monday through Friday. For neonates with a subscribed parent, a NICU team member will launch an ExtendedCare telehealth visit (“virtual room”) from the patient’s Epic chart. From ExtendedCare, a NICU team member will use the “invite” feature to invite the subscribed parent(s); the parents then receive a message to their email/cell phone that includes their child’s unique Extended Care link. The parent(s) can use this link, if desired, to enter the “virtual room.” If a parent joins, they will establish the live, bidirectional audio and visual connection. FCR will then proceed in usual fashion. Parents can participate in virtual FCR as much, or as little, as they choose. They can also participate in FCR in person (standard of care) or not participate at all.

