**QUALITATIVE INTERVIEWS:** The stakeholder engagement team members will assist with recruitment of the interview participants. Stakeholders or a research team member will recruit eligible interview participants. They will hand-deliver a flyer to the parents/guardians of eligible patients at the time of [i.e., 2 days before the anticipated] hospital discharge. Alternatively, since parents are not often at the bedside for in-person recruitment, they will send a secure message from StudyPages or make a phone call to invite participants to participate in an interview. Non-respondents will be contacted once 7 days later by a research coordinator through StudyPages. Clinician (e.g., nurses, physicians) interview participants will be identified by stakeholder or research team members. Recruitment emails or Secure Chat messages will be sent to the clinicians. Repeat email/message outreach will be made to the clinician non-respondents at 2 and 4 weeks following initial outreach. Participants will receive \$50 for participating in an interview. Interested participants will have one in-depth interview that lasts ~45 minutes. Interviews will be in-person when possible, but otherwise by telephone or videoconference. Interviews will be audio recorded, transcribed, and reviewed for accuracy by the interviewer. Transcriptions will be uploaded into ATLAS.ti.

**DELIVERY OF SURVEY:** Parents will be invited to complete their first survey at

**PROTOCOL TITLE: Virtual Family-Centered Rounds in the Neonatal Intensive Care Unit:  
A Randomized Clinical Trial**

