the time of [i.e., 2 days before the anticipated] discharge. If a neonate has two eligible parents, separate invitations will be sent to each parent. Recruitment will occur via giving them a packet at discharge. The packet will contain a recruitment letter (flyer), a scannable barcode (to access the survey electronically if preferred), a website link (another alternative to access the survey electronically if preferred), and a paper version of the survey. Alternatively, since parents are not often at the bedside for in-person recruitment, the research assistant will send a secure message/email from StudyPages or make a phone call to invite participants to participate in an interview. Parents can complete the survey themselves or verbally with the research assistant who will directly input verbal responses into REDCap. The research assistant will make 3 daily attempts of outreach and follow up with non-respondents 7 days later. If a survey is not returned within 21 days of discharge, the survey will be considered a non-response. The survey delivery process from a Secure Chat message/email or phone call will occur at 30, 60, and 90 days to administer the subsequent survey packets (with 3 daily attempts and follow-up 7 days later and a 21-day response time limit). Electronic surveys will be conducted in REDCap. Paper surveys will be kept in a locked box in the locked physician workroom until collected by a research assistant, who will transfer the data into REDCap and then destroy the paper copy. For parents with more than one neonate enrolled in the study (i.e., twins/multiples), the parents will only receive one survey packet per child. The survey will be sent to the parents at the time that one of their children first discharges from the NICU (and each subsequent 30 day period will be based off that first child's discharge date). For subsequent siblings discharged at later dates, a research assistant will use StudyPages to message/call parents to obtain the responses to (a) questions #1 and 2 of the 30-day survey and (b) question #1 of the 90-day survey. These questions relate to the outcomes of (a) 30-day revisit/readmission and (b) 90-day breastmilk feeding. The research assistant will directly input the responses into REDCap.

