**DATA COLLECTION:** Data collection will include daily weekday virtual FCR observations; parent surveys; and review of the EHR, incident reports, and helpdesk technical issues log. Outcomes (for Aims 1-3) will include the following: FCR parent attendance proportion (captured using weekday rounding observations), length of stay (captured using EHR data), breast milk feeding initiation and breast milk feeding at discharge (captured using EHR data) and at 90 days after discharge (captures via parent via parent/guardian survey), growth failure and growth velocity (captured using EHR data), time to first social work contact (captured using EHR data), temperature instability (captured from an existy NICU quality dataset), feeding difficulty (captured from an existy NICU quality dataset), central line-associated bloodstream infection (captured from an existy NICU quality dataset), central line days (captured from an existy NICU quality dataset), antibiotics days (captured from an existy NICU quality dataset), medical errors (captured using data from EHR, incident reporting system, and solicited reports), 30-day revisit and readmission (captured via EHR and survey) parent experience and family-centered care (captured via parent/guardian survey at discharge), parent activation (captured via parent/guardian survey at discharge), parent distress: depression and anxiety (captured via parent/guardian survey at 0, 30, 60, 90 days from discharge), parent sleep (captured via parent/guardian survey at 0, 30, 60, 90 days from discharge), and parent quality of life (captured via parent/guardian survey at 0, 30, 60, 90 days from discharge).

RE-AIM (Aim 3) implementation evaluation data collection will include the

**PROTOCOL TITLE: Virtual Family-Centered Rounds in the Neonatal Intensive Care Unit:  
A Randomized Clinical Trial**

following: subscribed vs. not subscribed parents among intervention-arm parents, heterogeneity of intervention effects (interactions between neonate/parent characteristics and the intervention effect), virtual FCR attempts with technical issues (sounds, video, other), trial-related 24/7 helpdesk line calls, ExtendedCare wait time when parent(s) join, ExtendedCare connection time, device model (e.g., iPhone, Android, etc.) that parent uses to connect to the ExtendedCare visit, interruptions requiring a break in rounds due to a delivery or new admission, and virtual FCR use with NICU parents post-trial (maintenance).

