Data will be collected from both the intervention and control arm subjects. The EHR access for data collection will only occur in a retrospective fashion. The interaction with the control arm group parents will therefore include an invitation via letter (flyer) to participate in the surveys. The observations of FCR will be conducted by either a research team member or a NICU team member who already participates in FCR as part of clinical care. The information being recorded from the observations is whether or not parent(s) are present at FCR, and if so, what type of attendance (in person vs. virtual).

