## STATISTICAL ANALYSIS PLAN

### Statistical methods for primary and secondary outcomes

Our primary analysis strategy will analyze all available data from participating family units and their members, with groups defined according to the randomized assignment (intervention versus control) for that family unit. We will use graphical and analytical descriptive statistics to summarize infant, parent, and family unit characteristics. We will use methods for clustered survey data to adjust confidence intervals for family units with multiple parental respondents. We will not use cluster-adjusted confidence intervals for family units with multiple infants unless the mean number of infants per family unit unexpectedly exceeds 1.10.

We will use generalized linear models to estimate intervention effect sizes and confidence intervals and to test hypotheses for outcomes. Independent variables will include a binary indicator for intervention assignment along with a parsimonious set of subject characteristics as covariates (parent age, race, ethnicity, gender, education, transportation security, marital status, other children dependents, digital literacy score). We will specify the generalized linear mixed models as linear, logistic, or Poisson regressions, according to the outcome type. Random effects will be specified to accommodate the multilevel structure of the data and the nesting of longitudinal measurements, when applicable, within parents and the nesting of parents and infants within family units.

To account for increased exposure among subjects with longer neonatal intensive care unit (NICU) stays when analyzing the primary outcome, we will use Poisson regression to compare rates for the family-centered rounds (FCR) parent attendance outcome between intervention vs. control group subjects, using the numerator for this outcome as the dependent variable and using the logarithm of the denominator as an offset term. We will also use Poisson

regression for analyzing the error rate outcomes, with the offset being the logarithm of the number of days in the NICU. The exponentiation of the Poisson regression coefficient for the treatment indicator will thus represent an adjusted between-arm rate ratio for FCR parent attendance.

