### **Methods for additional analyses (e.g. subgroup analyses)**

We will conduct mediation analysis to evaluate relationships between parent activation and the other secondary and exploratory outcomes. We will also evaluate relationships between FCR attendance and the other outcomes. For example, the intervention effect on HRQOL may be mediated by FCR attendance with a dose-response relationship. Thus, if we find a positive intervention effect on HRQOL, we will explore FCR attendance mediation using similar methods. We anticipate that the intervention effect on the following outcomes will be mediated by FCR attendance with a dose-response relationship: parent experience, family-centered care, parent activation, parent HRQOL, length of stay, and breastmilk feeding.

We will explore heterogeneity of the treatment effects, using rigorous analyses based on including interaction terms for the candidate effect modifier and the intervention effect term(s).

Candidate effect modifiers will include residence-to-NICU distance, neighborhood health conditions, parent race and ethnicity, parent transportation security, other children dependents, parent computer/smart device access, parent internet access, and parent digital literacy score. For these terms, each will be evaluated without correction for multiple discovery. Other candidate effect modifiers will be evaluated as part of a comprehensive examination of intervention effects and for these, we will control the false discovery rate at 10%.

We will decompose the FCR parent attendance outcome measure by the type of attendance to separate the in-person and virtual components. We will explore the type of attendance as an outcome variable and as a predictor of the secondary outcomes. We will include a statistical exploration within the intervention arm for whether higher virtual FCR attendance is associated with differences in in-person FCR attendance. Additionally, we will fit regression models for each secondary outcome that simultaneously include measures of both virtual and in-person FCR attendance, allowing us to assess and compare whether the incremental benefits of higher FCR attendance are similar between both types of attendance.

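### The digital literacy score in the primary model appears to be collected only at discharge, after exposure to virtual FCR and only from survey responders

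*Combined protocol and SAP*

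**What the plan says.** **Use of the score.** The covariate list in the SAP, Statistical methods for primary and secondary outcomes, ends with "transportation security, marital status, other children dependents, digital literacy score". The same section describes the primary result as an "adjusted between-arm rate ratio for FCR parent attendance", so these covariates enter the primary model. Under Methods for additional analyses, the candidate effect modifiers include "parent computer/smart device access, parent internet access, and parent digital literacy score".

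**Timing of parent data.** Protocol section 7, Delivery of survey, states: "Parents will be invited to complete their first survey at" "the time of [i.e., 2 days before the anticipated] discharge". A survey not returned within 21 days of discharge counts as a non-response. Later surveys follow at 30, 60 and 90 days. No enrolment or baseline survey is described.

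**Missing data.** The last SAP section makes complete-case analysis the primary strategy and keeps multiple imputation for sensitivity analysis. Protocol section 8 assumes 75% survey response for parent-reported outcomes. It also says that outcomes resting on rounds observation and the EHR will cover every subject.

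**The concern.** A covariate in the primary model should not be something the assigned arm can change. Virtual FCR means using an app on the parent's own phone or computer, with weekday invitations for subscribed families and a helpdesk. If digital literacy is scored at discharge, parents who used the app may score higher because they used it. Hypothesis 1a concerns the total effect of being offered virtual FCR on attendance, and conditioning on a consequence of assignment does not estimate that effect.

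The same timing weakens the effect-modifier analyses. A high-literacy group defined at discharge would hold, in the intervention arm, some parents who got there by using the app and, in the control arm, only parents who were there already. The two are not comparable, and the protocol's interest in the digital divide depends on that comparison.

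A second consequence does not depend on whether the arm changes the score. If a covariate exists only for survey responders, a complete-case adjusted model drops every non-responder, even for outcomes observed on all neonates.

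**Working it through.** **Step 1. When is the score measured?** Neither document gives an instrument, source or time for digital literacy, device access or internet access. The described routes are:

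- Data sources (section 7, Data collection): "Data collection will include daily weekday virtual FCR observations; parent surveys; and review of the EHR, incident reports, and helpdesk technical issues log". The outcome and RE-AIM lists that follow do not mention digital literacy.
- Research contact at assignment (section 7, Assignment): the coordinator opens the allocation to "invite parents of neonates assigned to the intervention arm to sign up for virtual FCR". This reaches one arm only.
- Control parents (section 7, Data collection): "The interaction with the control arm group parents will therefore include an invitation via letter (flyer) to participate in the surveys".

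The discharge survey is the first described route that could supply a parent-reported score in both arms. This is an inference by elimination.

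**Step 2. How much exposure comes before it?** Section 8 gives log length of stay as mean 3.0, SD 1.0. The geometric mean is exp(3.0) = 20.1 days. Under a lognormal distribution, P(stay ≥ 14 days) = 1 − Φ((ln 14 − 3.0)/1.0) = 0.64; the figure is 0.85 for 7 days and 0.48 for 21 days. About 36% of stays are under 14 days, so exposure before the survey is often weeks, but not always.

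**Step 3. Effect on the rate ratio (assumed inputs).** Let the intervention raise the score by g SD, and let each SD go with b higher log attendance. Adjusting for the score multiplies the rate ratio by exp(−g·b). This holds whether the score gain itself raises attendance (adjustment removes that part) or only marks prior literacy (adjustment over-corrects). The documents give neither g nor b.

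| g | b = 0.1 | b = 0.2 | b = 0.3 |
|---|---|---|---|
| 0.1 | 0.99 | 0.98 | 0.97 |
| 0.2 | 0.98 | 0.96 | 0.94 |
| 0.3 | 0.97 | 0.94 | 0.91 |

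A simulated Poisson model with offset agrees (429 neonates, 2:1, 400 runs; assumed b = 0.2, attendance 35% in controls at an average score, direct rate ratio 1.30). For g = 0, 0.1, 0.2 and 0.3 the unadjusted rate ratio was 1.30, 1.33, 1.36 and 1.39. The adjusted one stayed at 1.30. Check: 1.30/1.39 = 0.94 = exp(−0.3 × 0.2).

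**Step 4. Loss of non-responders.** First the plan's own figure. With δ = −ln 0.75 = 0.2877, SD 1.0, two-sided α = 0.05, 80% power and 2:1 allocation:

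- Control n = 1.5 × (1.960 + 0.842)² / 0.2877² = 142.3, rounded up to 143.
- Intervention n = 286; total 429; 429/0.96 = 446.9, so 447 randomised. The plan's number is reproduced.
- Power at 143:286 = Φ(0.2877/√(1/143 + 1/286) − 1.960) = 80.2%.

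Now apply 75% response, treating parents as neonates: 429 × 0.75 = 321.75, which the plan gives as 321 (107 control, 214 intervention).

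- Power at 107:214 = Φ(0.2877/√(1/107 + 1/214) − 1.960) = Φ(0.470) = 68%.

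The calculation ignores any precision gained from covariates. A neonate with two invited parents may have a score from either, so the loss could be smaller.

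**The case against.** The strongest reply is that the timing is nowhere stated. The survey forms are not in the documents, the text on control parents says that contact will include a survey invitation rather than consist only of one, and an EHR or enrolment source cannot be excluded. The SAP speaks of subject characteristics and never calls them baseline values. All of this stands, and it is why the point is put as what the documents appear to imply.

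The mechanism is plausible but not shown. Weekday links go only to subscribed parents, who may join as little as they like, so non-users and short-stay families have little exposure. If the app goes unused, g is near zero and there is no bias. With g and b positive, the bias runs towards no benefit, so it would not create a false positive for Hypothesis 1a. The modifier analyses are already described as exploring heterogeneity. These points limit the size but do not answer the question of timing.

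A reader might infer that the score is known to be taken after weeks of exposure in every family, or that transportation security and the other listed covariates are equally affected. The documents do not support either. Stays vary, only users are exposed, no pathway from virtual FCR to transportation security is described, and age, race, ethnicity and education are essentially fixed.

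**Conclusion.** The concern holds in limited form. Followed as written, the plan puts into its primary model a score that, on the only described route to both arms, is measured after randomisation, that the intervention could change, and that only responders would have. The same timing affects the literacy, device-access and internet-access modifiers.

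The bias in the attendance rate ratio is unknown and may be small: a factor of about 0.99 to 0.91 over the assumed range. The loss of about a quarter of neonates from the adjusted attendance and length-of-stay models may matter more. It rests on the covariates existing only for responders, on 75% response applying to them, and on one parent per neonate. It would also contradict the protocol's statement that these outcomes include all subjects.

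A reader might go further and conclude that the primary result would be invalid or would falsely favour virtual FCR. The documents do not support that, given the direction and likely size of the bias. Both problems would fall away for any covariate shown to be collected from all families before assignment is opened.

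**What to change.** **Statistical methods for primary and secondary outcomes.** Make the primary attendance model, and the other models for observation- and EHR-based outcomes, either unadjusted or adjusted only for characteristics fixed before randomisation and available for all randomised neonates. State the source and time of each covariate. Move the digital literacy score, and any other changeable item collected only in the discharge survey, to a sensitivity analysis unless it is shown to be collected before assignment is opened.

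**Methods for additional analyses.** Keep the literacy, device-access and internet-access analyses, but label them exploratory and measured after randomisation. Base the main digital-divide analysis on listed modifiers that the intervention cannot change: residence-to-NICU distance, neighbourhood conditions, and race and ethnicity.

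**Cost.** SAP wording only. Any precision gained from the removed covariates is lost, which is likely to be little, and three modifiers carry a weaker interpretation.

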### **Interim analyses**

Interim analyses will not be conducted during this trial.

### **Methods for additional analyses (e.g. subgroup analyses)**

We will conduct mediation analysis to evaluate relationships between parent activation and the other secondary and exploratory outcomes. We will also evaluate relationships between FCR attendance and the other outcomes. For example, the intervention effect on HRQOL may be mediated by FCR attendance with a dose-response relationship. Thus, if we find a positive intervention effect on HRQOL, we will explore FCR attendance mediation using similar methods. We anticipate that the intervention effect on the following outcomes will be mediated by FCR attendance with a dose-response relationship: parent experience, family-centered care, parent activation, parent HRQOL, length of stay, and breastmilk feeding.

We will explore heterogeneity of the treatment effects, using rigorous analyses based on including interaction terms for the candidate effect modifier and the intervention effect term(s).

Candidate effect modifiers will include residence-to-NICU distance, neighborhood health conditions, parent race and ethnicity, parent transportation security, other children dependents, parent computer/smart device access, parent internet access, and parent digital literacy score. For these terms, each will be evaluated without correction for multiple discovery. Other candidate effect modifiers will be evaluated as part of a comprehensive examination of intervention effects and for these, we will control the false discovery rate at 10%.

We will decompose the FCR parent attendance outcome measure by the type of attendance to separate the in-person and virtual components. We will explore the type of attendance as an outcome variable and as a predictor of the secondary outcomes. We will include a statistical exploration within the intervention arm for whether higher virtual FCR attendance is associated with differences in in-person FCR attendance. Additionally, we will fit regression models for each secondary outcome that simultaneously include measures of both virtual and in-person FCR attendance, allowing us to assess and compare whether the incremental benefits of higher FCR attendance are similar between both types of attendance.

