## 2) Objectives

The overall objective of this study is to test the efficacy of virtual family-centered rounds (FCR) compared to standard rounds for NICU patients and to conduct an intervention evaluation of the virtual FCR intervention.

**Aim 1: Evaluate the impact of virtual FCR on parental activation and wellbeing.** The primary outcome will be FCR parent attendance proportion (number of round encounters with a parent present – either virtually or in person – divided by total number of round encounters). Increased parent FCR attendance would increase the delivery of best practice. We will also compare parent experience (Child HCAHPS) and parent activation (P-PAM) at discharge and parent distress and quality of life at 0, 30, 60, and 90 days from discharge between assigned trial arms. Parent wellbeing promotes neonatal wellbeing.

- *Hypothesis1a: The virtual FCR (intervention) group will have a higher parent FCR attendance proportion compared to the standard FCR (control) group.*
- *Hypotheses1b: Parents of virtual FCR neonates will report (a) better experience, (b) higher activation, (c) less distress, and (d) better quality of life compared to parents of standard-of-care neonates.*

**Aim 2: Evaluate the impact of virtual FCR on neonatal outcomes.** We will compare breast milk feeding at discharge and 90 days from discharge, growth failure, medical errors, and NICU length of stay between assigned trial arms.

- *Hypotheses2: Virtual FCR neonates will have (a) greater breast milk feeding, (b) reduced growth failure, (c) fewer errors, and (d) shortened length of stay compared to standard-of-care neonates.*

**Aim 3: Conduct a mixed methods evaluation of the virtual FCR intervention.** We will measure all five RE-AIM dimensions using quantitative (chart review, surveys) and qualitative (observations, interviews) methods. Observations will be of NICU FCR; interviews will be with intervention arm parents and NICU providers. We will use a convergent design and merge data in the analysis and reporting phases.

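### Parent activation is measured once, around discharge, so the planned mediation analysis cannot tell an indirect effect on in-hospital outcomes from the stay itself having changed activation

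*Combined protocol and SAP*

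**What the plan says.** The SAP, under Methods for additional analyses, commits to this: "We will conduct mediation analysis to evaluate relationships between parent activation and the other secondary and exploratory outcomes". No outcome is left out, and neither a direction nor a time order is given. Mediation by rounds attendance is described separately in the sentences that follow.

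Protocol section 7 (Data collection) gives activation one source: "parent activation (captured via parent/guardian survey at discharge". Section 2 confirms the contrast with the repeated measures, placing experience and activation "at discharge and parent distress and quality of life at 0, 30, 60, and 90 days from discharge". No baseline or in-stay activation measure is described.

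Section 7 (Delivery of survey) opens the first survey at "the time of [i.e., 2 days before the anticipated] discharge" and closes it as follows: "If a survey is not returned within 21 days of discharge, the survey will be considered a non-response".

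The outcomes listed in section 7 include "length of stay (captured using EHR data"), "breast milk feeding initiation and breast milk feeding at discharge (captured using EHR data") and "growth failure and growth velocity (captured using EHR data"). They also include medical errors, line infection, line days, antibiotic days and time to first social work contact. The sample size text in section 8 treats medical errors as exploratory, which puts them within the scope of the mediation sentence.

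**The concern.** A mediation claim needs the mediator to act before the outcome. For in-hospital outcomes the only activation score is taken when the outcome is over or nearly over. A long or eventful stay could itself lower or raise a parent's activation. A model that regresses the outcome on arm and activation would read that reverse association as the second leg of an indirect path. Randomization protects the effect of arm on activation but not the link between activation and outcome. A larger sample does not help, because it only makes the spurious link more significant.

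At stake is the explanation the trial offers for its results: that virtual rounds act on stay, growth or errors by activating parents, when these data cannot show it.

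**Working it through.** **1. Timing of each outcome against the activation survey (day -2 to day +21 around discharge)**

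| Outcome | Position |
|---|---|
| Length of stay, growth, medical errors, line infection, line and antibiotic days, time to social work contact, breast milk initiation and feeding at discharge | Settled or nearly so |
| Parent experience, family-centered care, day-0 distress, sleep and quality of life | Same survey; order undetermined |
| 30-day revisit/readmission | Mixed: an event on day 5 precedes a survey returned on day 15 |
| 30-, 60- and 90-day distress, sleep and quality of life; 90-day breast milk feeding | After the survey |

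One exception: for multiples, section 7 times the survey to the first sibling's discharge, so it can precede part of a later sibling's stay.

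**2. The plan's own figure**

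Section 8 gives a log length-of-stay SD of 1.0, a 25% reduction of interest, 2:1 allocation, 80% power and two-sided 5%.
- Effect: -ln(0.75) = 0.2877.
- Controls: (1.960 + 0.842)² × (1 + 1/2) × 1.0² / 0.2877² = 142.3, so 143. With 286 intervention, the total is 429.
- With 4% attrition: 429 / 0.96 = 446.9, so 447. Both stated figures reproduce.
- Parent surveys: 429 × 0.75 = 321.75, stated as 321. At 2:1 this is 214 and 107.

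**3. Size of a false indirect effect on stay**

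Assumptions not in the documents: the intervention raises activation by *a* = 0.2 to 0.5 SD; one SD longer log stay changes activation by *r* = -0.1 to -0.3 SD. Neither arm nor activation affects stay, so the true indirect effect is zero.
- Arm-to-activation path: estimate *a*, standard error √(1/214 + 1/107) = 0.118.
- Activation-to-stay path given arm: estimate *r* (both variables have unit SD within arm), standard error √(1 - r²) / √321.
- Apparent indirect effect on log stay: *a* × *r*. Apparent reduction in stay: 1 - exp(*a* × *r*).
- Chance that both paths are significant: approximately the product of the two powers.

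| *a* | *r* | z, first path | z, second path | Both significant | Apparent reduction |
|---|---|---|---|---|---|
| 0.2 | -0.1 | 1.69 (power 39%) | 1.80 (44%) | 17% | 2.0% |
| 0.333 | -0.2 | 2.81 (80%) | 3.66 (95.5%) | 77% | 6.4% |
| 0.5 | -0.3 | 4.22 (99%) | 5.63 (100%) | 99% | 13.9% |
| 0.2 to 0.5 | 0 | 39% to 99% power | 5% | 2% to 5% | 0 |

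The middle row uses roughly the activation difference detectable with 80% power at 214 against 107. Simulation agrees: 16% to 99% over the grid and about 77% at the middle setting. If longer stay raises activation, the false effect changes sign.

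**4. Other scenarios, by simulation (*r* = -0.1, -0.2, -0.3, -0.4, assumed)**
- Arm shortens stay by 25%, with no direct effect on activation: 2%, 6%, 11% and 16% of trials declare false mediation.
- Arm shortens stay by 25% and directly raises activation by 0.3 SD: 35%, 81%, 90% and 94%, with an apparent mediated share of about 12%, 25%, 40% and 58%.

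The problem is greatest when the intervention does activate parents, which is what section 2 hypothesizes.

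**5. Does a false mechanism become a false claim about stay?**

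In the null scenario of step 3, the randomized comparison falsely favors the intervention in about 2.5% of trials. At the middle setting 0.77 × 0.025 = 1.9% of trials show both errors. Over the grid the figure is about 0.4% to 3%.

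**The case against.** **The SAP does not say outright that activation is the mediator.** True: the sentence speaks of relationships, and where the section names length of stay the mediator is attendance, which accrues during the stay. Activation also appears there as an outcome of attendance. Still, attendance mediation is set out separately, and a mediation analysis centered on activation most naturally makes it the mediator. Apart from medical errors, the documents also do not list which outcomes are secondary or exploratory. If another meaning was intended, the SAP needs to say so.

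**Discharge activation may stand in for activation during the stay.** This is fair. When a construct is measured is not the same as when it acts, so the timing does not prove that mediation is impossible. But the SAP does not make this argument, and one score cannot separate it from reverse causation.

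**The size rests on assumed inputs.** This also stands. Both paths and the sign of the reverse path are unknown, and the rate falls to 2% to 16% when the arm does not directly raise activation. The figures show that the error can be large; they do not predict its size.

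**A reader might infer that the plan would falsely report shorter stays.** The documents do not support that. Length of stay is also compared directly between randomized arms, and step 5 shows that few null trials would carry both errors. In its quality-of-life example the SAP looks for a mediator only after finding an intervention effect. That condition is written for attendance, not activation, but a null arm comparison would be visible to any reader.

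**These are additional analyses.** This limits the consequences, but exploratory status does not supply the missing time order.

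**Conclusion.** The concern holds for in-hospital outcomes, and the order is also undetermined for outcomes collected on the same discharge survey. With a single activation score taken between two days before anticipated discharge and 21 days after it, an indirect effect on these outcomes cannot be told from reverse causation. Under the assumed inputs a spurious indirect effect on stay is jointly significant in roughly 16% to 99% of trials, against 2% to 5% with no reverse path. The timing argument rests on the documents; the rates rest on assumptions.

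The harm is a false account of mechanism. The primary attendance outcome, the randomized arm comparisons and the sample size are unaffected. Two further readings go too far: that every in-hospital outcome is complete when activation is recorded (parents answering before discharge and later-discharged siblings are exceptions), and that every 30-day revisit or readmission safely follows the survey. A change to the SAP is warranted because it is specific and nearly free.

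**What to change.** State in the SAP that activation is the mediator, and limit that analysis to outcomes occurring after the survey is completed:
- distress, sleep and quality of life at 30, 60 and 90 days;
- breast milk feeding at 90 days;
- 30-day revisits and readmissions only when they occur after that parent's survey completion date.

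Report activation's relation to in-hospital outcomes, and to outcomes on the same discharge survey, as associations without indirect effects. State the no-confounding assumption for the analyses that remain, since correct time order alone does not secure it.

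The cost is a short SAP edit and fewer models. The revisit rule needs a survey completion date and an event date; a parent-reported revisit without a date could not be placed. The downside is that no activation-mediation claim can be made for in-hospital outcomes.
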